5.3.7. Pharmacokinetics

Darunavir

The pharmacokinetic (PK) properties of DRV, co-administered with RTV, have been evaluated in healthy adult volunteers and in HIV-1 infected patients. Exposure to DRV was higher in HIV-1 infected patients than in healthy subjects. The increased exposure to DRV in HIV-1 infected patients compared to healthy subjects may be explained by the higher concentrations of α 1-acid glycoprotein (AAG) in HIV-1 infected patients, resulting in

higher DRV binding to plasma AAG and, therefore, higher plasma concentrations. DRV is primarily metabolized by CYP3A. RTV inhibits CYP3A, thereby increasing the plasma concentrations of DRV considerably.

Absorption

DRV was rapidly absorbed following oral administration. Maximum plasma concentration (Cmax) of DRV in the presence of low dose RTV is generally achieved within 2.5-4.0 hours (h). The absolute oral bioavailability of a single 600 mg dose of DRV alone was approximately 37% and increased to approximately 82% in the presence of 100 mg twice daily RTV. The overall PK enhancement effect by RTV was an approximate 14-fold increase in the systemic exposure of DRV when a single dose of 600 mg DRV was given orally in combination with RTV at 100 mg twice daily. When administered without food, the relative bioavailability of DRV in the presence of low dose RTV is lower as compared to intake with food. The type of food does not affect exposure to DRV.

Distribution

DRV is approximately 95% bound to plasma protein. DRV binds primarily to plasma AAG. Following intravenous administration, mean (\pm SD) the volume of distribution of DRV alone was 88 (\pm 59) L and increased to 131 (\pm 50) L in the presence of 100 mg twice-daily RTV.

Biotransformation

In vitro experiments indicate that DRV primarily undergoes extensive oxidative metabolism by the hepatic cytochromes (CYP) system and almost exclusively by CYP3A4. At least 3 oxidative metabolites of DRV have been identified in humans; all showed activity that was at least 10-fold less than the activity of DRV against wild type HIV.

Elimination

After a 400/100 mg 14C-DRV with RTV dose, approximately 79.5 and 13.9% of the administered dose of 14C-DRV could be retrieved in feces and urine, respectively. Unchanged DRV accounted for approximately 41.2 and 7.7% of the administered dose in feces and urine, respectively. The terminal elimination half-life (t1/2) of DRV was approximately 15 h when combined with RTV. The intravenous clearance (CL) of DRV alone (150 mg) and in the presence of low dose RTV was 32.8 L/h and 5.9 L/h, respectively.

Ritonavir

PK of RTV have been studied in healthy volunteers and HIV-1 infected patients.

Absorption

The absolute bioavailability of RTV has not been determined.

After a single 600 mg dose, total system exposure was 13% higher when administered with a meal.

Metabolism

Nearly all of the plasma radioactivity after a single oral 600 mg dose of 14C-RTV oral solution was attributed to unchanged RTV. Five (5) RTV metabolites have been identified in human urine and feces. The isopropylthiazole oxidation metabolite (M-2) is the major metabolite and has antiviral activity similar to that of parent drug; however, the concentrations of this metabolite in plasma are low. In vitro studies utilizing human liver microsomes have demonstrated that CYP3A is the major isoform involved in RTV metabolism, although CYP2D6 also contributes to the formation of M-2.

Elimination

In a study of 5 subjects receiving a 600 mg dose of 14C-RTV oral solution, about 11% of the dose was excreted into the urine, with about 2 to 5% of the dose excreted as unchanged parent drug. In that study, more than 80% of the dose was excreted in the feces with about 20 to 40% of the dose excreted as unchanged parent drug. Upon multiple dosing, RTV accumulation is less than predicted from a single dose possibly due to a time and dose-related increase in clearance.

Cobicistat

COBI is a mechanism-based CYP3A inhibitor and pharmacokinetic (PK) enhancer. COBI chemical structure is closely related to ritonavir and, as a result, it shares some of its characteristics.

Absorption

07-11-2016

In a trial where subjects were instructed to take co-administered COBI and darunavir with food, median COBI peak plasma concentrations was observed 3.5 hours (h) post-dose.

Steady-state COBI Cmax, AUC_{0- τ} and C τ (mean ± SD), values were 0.99 ± 0.3 µg/mL (n=60), 7.6 ± 3.7 µg.h/mL (n=59), and 0.03 ± 0.1 µg/mL (n=59), respectively.

A food effect trial was not conducted for COBI since it is coadministered with other antiretroviral agents under fed conditions, in accordance with the prescribing information for these agents. It is recommended that COBI coadministered with atazanavir or darunavir be administered with food.

Metabolism

COBI is metabolized by CYP3A and to a minor extent by CYP2D6 enzymes and does not undergo glucuronidation. COBI 150 mg provides near-maximal inhibition of CYP3A, as assessed using midazolam. These results were roughly in agreement with those obtained with ritonavir (in vitro studies utilizing human liver microsomes have demonstrated that CYP3A is the major isoform involved in RTV metabolism, although CYP2D6 also contributes to its biotransformation.

Overall, COBI a lower potential for off-target drug interactions than the standard boosting agent ritonavir, due to its more selective inhibition of CYP3A and lower likelihood for enzymatic induction, and is devoid of anti-HIV activity.

Elimination

The terminal plasma half-life of cobicistat following administration of COBI is approximately 3 to 4 h which is slightly lower than ritonavir (3 to 5 h). With single dose administration of 14C COBI after multiple dosing of COBI for 6 days, the mean percent of the administered dose excreted in feces and urine was 86.2% and 8.2%, respectively.

ABX464

After single oral administration of 50 to 200 mg ABX464, ABX464 is relatively quickly absorbed and undergoes a very extensive biotransformation into its N-glucuronide metabolite, NGIc.

In most of the subjects, regardless of the dose, ABX464 plasma concentrations is generally not measured after 8 to 10 h post-dose. Cmax is generally observed within the first 2 h post-dose and then ABX464 plasma concentrations decreased with a t1/2 of about 1 to 2 h.

NGlcABX464 plasma concentrations were markedly higher than those of the parent drug with mean Cmax about 200 to 300-fold higher than ABX464 Cmax. Cmax was observed around 4 h post-dose with a very limited variability thereafter ABX464NGlc was slowly eliminated and had a t1/2 of 90 to 110 h.

Relationship between rate and extent of absorption of ABX464 and ABX464 dose is quite erratic with a reduced increase with the dose up to 150 mg and a saturation like behavior at 200 mg.

NGIcABX464 exposure-dose relationship is somehow comparable to that of ABX464 although increase of Cmax and AUCs tend to be dose proportional between 50 and 150 mg.

Since ABX464 undergoes a high level of biotransformation, ratios between metabolite and parent drug appear to be unchanged across the studied dose range but inter-individual variability prevented from definite conclusions.

Therefore, ABX464 should rather be considered as a pro-drug with regard to its short t1/2. Its metabolite, ABX464NGIc exhibits markedly higher blood concentrations and has a much longer t1/2 which could be of pharmacological interest. Last, dose-exposure relationship appears erratic between 50 and 200 mg but tends to linearity up to 150 mg.

PK Study Design

The main objective of the PK analysis is to evaluate the impact of concomitant administration of ABX464 on DRV and RTV/COBI PK characteristics.

Considering that DRV/RTV or DRV/COBI is a chronic treatment, it is deemed more relevant to evaluate the possible drug-drug interaction at steady-state.

With regard to the relatively short $t_{1/2}$ of DRV (15 h), steady-state is expected to be reached between the 3rd and the 4th day of administration. RTV and COBI have a lower $t_{1/2}$ and thus will not require a longer treatment duration to be at steady-state.

ABX464 was shown to have a very short $t_{1/2}$ (1 to 2 h), so steady-state is virtually reached at the second administration, while NGIcABX464 has a $t_{1/2}$ of 90 to 110 h, meaning that steady-state is reached after 19 to 22 days of administration. Therefore, PK blood collection is planned to be done on Day 25 (25 days after initiation of ABX464 administration). Collection of sparse pre-dose samples from Day 1 o Day 25 will allow to control that NGIcABX464 is at steady-state at the time of PK assessment and to check if steady-state pre-dose levels of DRV and RTV are maintained with co-administration of ABX464.

Since PK analysis is done at steady-state, PK blood sampling will be limited to the higher dosing interval and expression of the extent of exposure of each compound will be determined by AUC_{0-τ} (with τ =24 h for ABX464 and NGIcABX464 and 12 h for DRV and RTV).

A first blood sample (reference) for DRV and RTV/COBI will be collected on the first day of treatment before any drug administration then blood samples will be collected for PK purpose at the following days:

- Day 0 pre DRV/RTV-COBI morning dose*;
- Day 7 pre DRV/ RTV-COBI morning dose;
- Day 14 pre DRV/ RTV-COBI morning dose;
- Day 21 pre DRV/ RTV-COBI morning dose;

Day 25** pre DRV/ RTV-COBI morning dose, 0.5, 1, 1.5, 2, 2.5, 3, 3.5, 4, 6, 8, 12, and 24 h post-dose;

- * reference for DRV and RTV-COBI;
- ** could be performed at Day 21 or Day 28 according to the allowed time window

A total of 17 blood samples per patient will be collected for PK purpose and sent to ATLANBIO for Bioanalyses.

Blood samples for determination of ABX464, NGIcABX464, and/or DRV and RTV-COBI blood levels will be collected from all patients using direct venipuncture or an indwelling catheter.

Then, the following PK parameters will be derived for ABX464, NGIcABX464, DRV, and RTV-COBI Day 25 for each patient:

- Cmax, tmax: the maximum plasma concentration (Cmax) and the time taken to reach Cmax (tmax) will be obtained directly from the concentration-time data.
- AUC_{0-τ}: the area under the concentration-time curve from time zero to the time of dosing interval τ (24 h post-dose for ABX464 and NGIcABX464, and 12 h post-dose for DRV and RTV). If no concentration can be measured at this time point, AUCO-last (from time zero to the last quantifiable concentration) will be calculated. Both parameters will be presented independently. For both parameters, a linear trapezoidal method will be used.

Moreover, evaluation of steady-state will be made by visual inspection of the pre-dose concentration measurement collected over the study duration.

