9.2.1. Pharmacokinetics

A total of 22 blood samples per patient will be collected for PK purpose.

Individual plasma concentrations of ABX464, NGIcABX464, DRV, and RTV or COBI will be presented by treatment and time points. Descriptive statistics for the plasma concentrations will be presented as number of available data (N), mean, standard deviation (SD) and will be calculated if at least 2/3 of the plasma values per time-point are above LOQ (i.e. $N \ge 10$ if 15 patients are available for a given group). For descriptive statistics calculations, BLQ concentrations below the limit of quantification will be set to zero (0) if they are reported before the first quantifiable sample or considered as missing data if they are reported after the first quantifiable data.

Then, the following PK parameters will be derived for ABX464, NGIcABX464, DRV, and RTV Day 53 for each patient:

 C_{max} , t_{max} : the maximum plasma concentration (C_{max}) and the time taken to reach C_{max} (t_{max}) will be obtained directly from the concentration-time data.

AUC_{0- τ}: the area under the concentration-time curve from time zero to the time of dosing interval τ (24 h post-dose for ABX464 and NGIcABX464, and 12 h post-dose for DRV and RTV). If no concentration can be measured at this time point, AUC0-last (from time zero to the last quantifiable concentration) will be calculated. Both parameters will be presented independently. For both parameters, a linear trapezoidal method will be used.

Individual derived PK parameters will be presented by treatment and day of PK assessment when appropriate. Descriptive statistics of the PK parameters will be presented as N, mean, SD, coefficient of variation (CV %), median, minimum (Min), maximum (Max) values, and geometric mean (GM).

In the tables of individual PK parameters, all the deviations from planned analysis will be mentioned by flagging the abnormal results.

Possible exclusion of flagged PK parameters could be performed if, in the judgment of the pharmacokineticist, they are deemed not to be "pharmacokinetically relevant". Exclusion of PK parameters will be discussed in the PK results section. If data are excluded from the PK dataset, all subsequent statistical analyses will be performed twice, once using the complete available PK dataset and once using the final PK dataset as defined by the pharmacokineticist. Study conclusion will be based on the final dataset as defined by the pharmacokineticist.

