For each compound, plasma concentration vs. time curves will be presented on a log-linear scale:

- mean plots showing the data of both treatments (administration alone and co-administration with ABX464);
- by patient plots with the treatments on separate plots (spaghetti plots).

Formal PK Statistics

It is assumed that all PK data of DRV and RTV/COBI obtained with co-administration of placebo will be gathered in a placebo group accounting for a theoretical total of a minimum of 7 patients.

Evaluation of drug-drug interaction

The relative bioavailability (F_{rel}) after multiple dose administration with either co-administration of ABX464 or of placebo will be evaluated on PK parameters determined on Day 25.

The comparison will be performed on Cmax and AUC_{0-t} using a 1-way ANOVA model with treatment as main effect on logarithmically transformed data. For each parameter, a point estimate for the ratio of geometric means (DRV/RTV or COBI with 50 mg ABX464 / DRV/RTV-COBI with placebo) will be obtained by calculating the difference of least square means on the logarithmic scale and subsequent back transformation with the exponential function. Likewise, 90% confidence interval for the ratios will be obtained by back transforming the 90% confidence intervals of least square mean differences on log-transformed PK parameters.

Moreover, evaluation of steady-state will be made by visual inspection of the pre-dose concentration measurement collected over the study duration.

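### Darunavir and ritonavir trough levels are to be checked as maintained, but the trough has no ratio, interval or criterion; the formal comparison covers only Cmax and a 12 h AUC

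*Protocol*

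**What the plan says.** Section 5.3.7 (PK Study Design) and the synopsis give the pre-dose samples two jobs. They confirm that the metabolite NGlcABX464 is at steady state, and they serve "to check if steady-state pre-dose levels of DRV and RTV are maintained with co-administration of ABX464". Samples are drawn before the morning dose on Days 0, 7, 14, 21 and 25. Day 0 is labelled the reference for darunavir (DRV) and ritonavir/cobicistat (RTV/COBI).

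Sections 5.3.7 and 9.2.1 both say that "evaluation of steady-state will be made by visual inspection of the pre-dose concentration measurement collected over the study duration". Section 9.2.1 adds summaries by treatment and time point: "Descriptive statistics for the plasma concentrations will be presented as number of available data (N), mean, standard deviation (SD").

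Interaction has its own paragraph in section 9.2.1. Cmax and AUC from Day 25 are compared "using a 1-way ANOVA model with treatment as main effect on logarithmically transformed data", giving "a point estimate for the ratio of geometric means" for "DRV/RTV or COBI with 50 mg ABX464 / DRV/RTV-COBI with placebo". The "90% confidence interval for the ratios will be obtained by back transforming the 90% confidence intervals of least square mean differences". Pre-dose concentration is not among the parameters. The AUC window is "12 h post-dose for DRV and RTV", whereas section 6.9.1 has both drugs given once a day.

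**The concern.** The main PK objective in section 5.3.7 is the effect of ABX464 on DRV and RTV/COBI pharmacokinetics. Saying that trough levels are maintained is a statement about how large a change can be ruled out. Means, SDs and a look at plots do not give that, because nothing states what fall the data exclude or what fall would matter.

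The formal analysis does not fill the gap indirectly. Cmax falls early in the interval, and the 12 h AUC leaves the second half of a once-daily interval out of every formal comparison. Until Day 28 the boosted protease inhibitor is the patients' only background antiretroviral regimen, so a fall in trough is the direction of interest.

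**Working it through.** The protocol states no power or precision for any PK comparison, so there is no figure of its own to reproduce. The 80% power in section 9.4 is for time to viral rebound and does not bear on this point.

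**1. What each measure receives under the plan**

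| Measure (DRV, RTV/COBI) | Descriptive summary | Ratio with 90% CI | Criterion |
|---|---|---|---|
| Cmax, Day 25 | yes | yes | none |
| AUC to 12 h, Day 25 | yes | yes | none |
| Pre-dose level, Days 0 to 25 | N, mean, SD, plus visual inspection | no | none |

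**2. Do Cmax and the 12 h AUC stand in for trough?** I used a one-compartment oral model at steady state. The model and the 25% rise in clearance are assumptions for illustration. The inputs from section 5.3.7 are a DRV half-life of 15 h and a tmax of 2.5 to 4.0 h; dosing every 24 h is from section 6.9.1.

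C(t) ∝ ka/(ka − ke) × [e^(−ke·t)/(1 − e^(−24ke)) − e^(−ka·t)/(1 − e^(−24ka))], with ke = ln 2/15 = 0.0462 per h and ka set to give a tmax of 3 h. A 25% rise in clearance makes ke = 0.0578.

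- Cmax falls by about 13%.
- AUC 0–12 h falls by about 16%.
- AUC 0–24 h falls by 1 − 1/1.25 = 20%.
- Trough falls by about 31%.

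Hand check of the trough, ignoring absorption: e^(−1.109)/(1 − e^(−1.109)) = 0.330/0.670 = 0.493 before, and e^(−1.386)/(1 − e^(−1.386)) = 0.250/0.750 = 0.333 after. The ratio is 0.68, a fall of about 32%. Moving tmax across 2.5 to 4.0 h changes each result by about one percentage point.

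**3. What precision is available from samples already planned?** The documents give no DRV or RTV trough variability, so I assume a within-patient log-SD (s) of 0.25, 0.35 and 0.45. Section 9.4 gives 21 ABX464 and 7 placebo patients at a dose level.

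SD of log(Day 25/Day 0) = s√2 = 0.354, 0.495, 0.636.

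- Within the ABX464 arm, the 90% half-width is t(0.95; 20) × s√2/√21, with t = 1.725: 0.133, 0.186, 0.240. The interval is the estimate ×/÷ **1.14, 1.20, 1.27**.
- For the ABX464/placebo ratio of changes, the half-width is t(0.95; 26) × s√2 × √(1/21 + 1/7), with t = 1.706 and the root 0.436: 0.263, 0.369, 0.474. The interval is ×/÷ **1.30, 1.45, 1.61**.

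**4. Which on-treatment days can be used?** The half-life of NGlcABX464 is 90 to 110 h. The fraction of steady state reached after d days is 1 − 2^(−24d/t½).

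| Day | t½ = 90 h | t½ = 110 h |
|---|---|---|
| 7 | 73% | 65% |
| 14 | 93% | 88% |
| 21 | 98% | 96% |
| 25 | 99% | 98% |

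If the metabolite drives any effect, averaging Day 7 and Day 14 into the on-treatment value would dilute it. The Day 25 visit may fall on Day 21 (section 5.2.4), which is still close to steady state.

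**5. Handling of low values.** Section 9.2.1 treats concentrations below quantification as missing when they follow the first quantifiable one. If that rule were applied to the pre-dose series, it would remove the lowest on-treatment troughs and push the mean upward.

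**The case against.** A reader might infer three stronger things, and the documents support none of them.

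- **That trough gets no estimate at all.** Section 9.2.1 plans N, mean and SD by treatment and time point, and section 9.2 allows confidence intervals where relevant. What is missing is a ratio, its interval and a criterion.
- **That seeing no change will be taken as no interaction.** No section says so. Interaction has its own formal analysis, and the visual-inspection sentence speaks of steady state. On that reading, however, the stated check on DRV and RTV levels has no evaluation method beyond the summaries.
- **That the sample misses relevant falls.** The protocol defines no relevant fall. With assumed CVs of 30 to 60%, a two-sided 5% between-arm test on Day 25 trough (21 v 7) would miss a 30% fall 24% to 71% of the time, but that test is not planned and ignores Day 0. A paired Day 0 to Day 25 test in 21 patients would miss it 4% to 49% of the time, and a 50% fall at most 3%.

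The fairest remaining defence is that section 9 leaves technical detail to the statistical analysis plan, which is not shown, and that the bound could be set there. That is true of the bound. But the protocol itself names both the method for the pre-dose series and the parameters for the formal comparison, and trough is absent from the latter. It is also true that PK is a secondary objective in a trial of 28 to 36 patients, and that viral load is measured at least weekly on treatment, so loss of suppression would be seen directly. Both limit the consequence; neither answers the trough question.

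**Conclusion.** The point holds as a gap in method. The protocol sets a check on DRV and RTV troughs and equips it only with descriptive summaries and inspection of plots, while the ratio with 90% CI is confined to Cmax and a 12 h AUC. In the model above, those two measures move by roughly half as much as trough or less (about 13% and 16% against 31%) when clearance rises by 25%.

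It is an inexpensive improvement to a secondary objective and does not undermine the trial. The size rests on an assumed one-compartment model and assumed within-patient log-SDs. The precision range should not be carried over to COBI: section 5.3.7 prints its trough as 0.03 ± 0.1 µg/mL, a CV of 0.1/0.03, about 330% as printed. The n = 21 figures apply to DRV at one dose level. RTV and COBI split the patients, and after escalation only about 6 of the first 8 patients would be on ABX464 50 mg, the only dose named in the formal ratio.

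**What to change.** In section 9.2.1:

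- Keep visual inspection for NGlcABX464 steady state.
- Add the pre-dose (or 24 h) concentration from the Day 25 PK visit to the log-scale analysis. Report the geometric mean ratio to the patient's own Day 0 reference by arm, and the ABX464/placebo ratio of those changes, each with a 90% CI. Do this for DRV, and separately for RTV and COBI where numbers allow, for each ABX464 dose group analysed.
- Show Days 7 and 14 by time point and do not pool them with Day 25.
- State how on-treatment troughs below quantification are handled, so that they are not dropped as missing.
- Describe levels as maintained only if the lower 90% limit lies above a bound the sponsor fixes before unblinding. Otherwise report the largest fall not excluded.
- Reconcile the 12 h AUC window with the once-daily regimen in section 6.9.1. The synopsis also refers to twice-daily administration when discussing RTV and COBI steady state.

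The cost is a few lines of text and one extra model per compound, on samples already planned. The downside is that with about 7 placebo patients, and fewer per booster, the between-arm interval will be wide and may have to be reported as inconclusive.

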5.4. Summary of blood samples

The Table 2 below summarizes the volume of blood to be sampled at each study visit.

Summary of Maximal Blood Volume (mL)	
Day - 21	26 mL + 60 ml (TILDA)
Day O	23 mL + 30 ml (reservoirs)
Day 7	24 mL
Day 14	24 mL
Day 21	24 mL
Day 25	52 mL
Day 28	24 mL + 30 ml (reservoirs)
TOTAL	317 mL
Follow-up (every week) - Reservoir and genotyping at Viral Rebound only	20 ml + 90 ml (TILDA and reservoirs) + 2 ml genotyping
Follow-up visit post ARTs reintroduction	15 mL

Laboratory testing	Tube	Volume (ml)
Glucose	Fluoride (2 cc)	2
Biochemistry	Heparin blood (6 cc)	6
Hematology	EDTA (3 cc)	3
H8V, HCV, HIV screen	Clotted blood (6 cc)	6
HIV RNA	EDTA (6 cc)	6
HIV Reservoir / TILDA	EDTA tube (7 cc) for PBMC collection	30 / 60
CD4 and CD8	EDTA (3 cc)	3
PK (per time point)	Heparin blood (4 cc)	4

